5.2.1.3.4 Dinaciclib Dose Evaluation

During Dose Evaluation, the first 12 subjects will receive pembrolizumab 200 mg on Day 1 of each cycle and Dose Level 0 of dinaciclib as described in Table 3 and Table 11.

Table 11 Dinaciclib Dose Levels

Dose Level	Dose of Dinaciclib
Level 0	C1D1: 7 mg/m ² ; C1D8: 10 mg/m ² ; C2D1+: 14 mg/m ²
Level -1	C1D1: 7 mg/m ² ; C1D8: 10 mg/m ² ; C2D1+: 10 mg/m ²
Level -2	C1D1: 7 mg/m ² ; C1D8: 7 mg/m ² ; C2D1+: 7 mg/m ²
C1D1: Cycle 1 Day 1 C1D8: Cycle 1 Day 8 C2D1+: Cycle 2 Day 1 and beyond.	

DLTs observed in Cycle 1 and Cycle 2 will be used to evaluate the dose level. If 4 or fewer subjects at Dose Level 0 have a DLT, the Signal Detection phase of the trial will be opened. Table 12 below summarizes the probabilities of observing the numbers and percentages of subjects under different assumptions of true DLT rate θ_0 , which can be interpreted as the one-sided p-values for testing the null hypothesis that the true DLT rate is less than θ_0 . These criteria are considered non-binding guidelines; recommendations would not be based solely on statistical grounds, as many other factors (ie, all aspects of the data from the trial) may be part of the decision process.

Table 12 Probability of Observing the Number (%) of Subjects with DLT

Observed Number (%) of Subjects	Probabilities (p-values) Under Different Assumptions				
	$\theta_0 = 0.20$	$\theta_0 = 0.25$	$\theta_0 = 0.30$	$\theta_0 = 0.35$	$\theta_0 = 0.40$
2 (16.7%)	0.442	0.609	0.747	0.849	0.917
3 (25.0%)	0.205	0.351	0.507	0.653	0.775
4 (33.3%)	0.073	0.158	0.276	0.417	0.562
5 (41.7%)	0.019	0.054	0.118	0.213	0.335
6 (50.0%)	0.004	0.014	0.039	0.085	0.158

The probabilities (p-values) for the monitoring of the first 12 subjects were calculated from Binomial distribution.

If there are ≥ 5 subjects with DLTs within the initial 12 subjects at Dose Level 0, up to 24 additional subjects may be enrolled using a design based on Ji et al. [32] (Table 13). If the monitoring guidance indicates escalation (“E”) from Dose Level -1 to Dose Level 0, a maximum of 5 additional subjects will be evaluated at Dose Level 0, up to 17 subjects in all. Therefore, a minimum of 12 subjects (Dose Level 0), and although highly unlikely, a maximum of 41 subjects evaluable for DLT assessment (up to 17 at Dose Level 0 plus 12 each at Dose Levels -1 and -2), may be needed for Dose Evaluation. The pembrolizumab dose will not be changed.

If ≥ 5 subjects with DLTs are observed at Dose Level 0, the dose level of dinaciclib will be reduced (Table 11) to Level -1 ($7 > 10 > 10$ mg/m²) to begin a new cohort of 3 subjects. Using Table 13, starting at the upper left corner, monitor the number of subjects and if the number of subjects/DLTs at Dose Level -1 reaches a “D” (de-escalate), then the dose level will be reduced to Level -2, and a cohort of 3 subjects will be enrolled at that dose level and monitored using Table 13 starting at the upper left corner (ie, the first 3 subjects at Dose Level -2).

At Dose Level -2, an “E” (escalate) would trigger an increase to Level -1, and enrollment and evaluation will continue at Level -1 from where it previously left off.

At Dose Level -1, an “E” (escalate) would trigger an increase to Level 0 and would resume at the number of subjects where it previously left off, or if it stopped at 12, would continue from subjects 13 up to 17. There is no dose escalation above Dose Level 0.

If the dinaciclib dose level is reduced to below Level 0, due to the potential complexity of trying to ensure balanced distribution of tumor types across the enrollment groups for dose evaluation, there are no restrictions regarding the minimum or maximum number of subjects

with CLL, MM, or DLBCL enrolled in these cohorts. This (no restriction) also applies if the dose is resumed back to Level 0.

All decisions regarding dose levels for subject enrollment and dosing will be made by the Sponsor and communicated to the investigators.

Note that while 30% is the target DLT rate used to generate the dose-adjustments in [Table 13](#), the observed rate of DLTs at the maximum tolerated dose may vary slightly above or below 30%.

Table 13 Monitoring Guidance in Dose Evaluation (Target DLT Rate of 30%)

	Number of Subjects Treated at Current Dose Level ^a															
	3	4	5	6	7	8	9	10	11	12		13 ^a	14 ^a	15 ^a	16 ^a	17 ^a
0	E	E	E	E	E	E	E	E	E	E	E	E	E	E	E	E
1	S	E	E	E	E	E	E	E	E	E	E	E	E	E	E	E
2	D	S	S	S	S	E	E	E	E	E	E	E	E	E	E	E
3	DU	DU	D	S	S	S	S	S	S	S	E	E	E	E	E	E
4		DU	DU	DU	D	D	S	S	S	S	S	S	S	S	E	E
5			DU	DU	DU	DU	D	D	S	S	S	S	S	S	S	S
6				DU	DU	DU	DU	DU	DU	D	D	S	S	S	S	S
7					DU	DU	DU	DU	DU	DU	DU	DU	D	D	S	S
8						DU	DU	DU	DU	DU	DU	DU	DU	DU	DU	D
9							DU	DU	DU	DU	DU	DU	DU	DU	DU	DU
10								DU	DU	DU	DU	DU	DU	DU	DU	DU

E = Escalate to the next higher dose level.

S = Stay at the current dose level.

D = De-escalate to the next lower dose level.

DU = Current dose level is unacceptably toxic.

Target DLT rate = 30%; a=.05, b=.05, k1=1.25; k2=0.5; pow=1.

Source: Ji et al. 2007) [32]

^a A maximum of 12 subjects will be used to evaluate Dose Levels -1 and -2; subjects 13-17 are only used to evaluate Dose Level 0 if ≥ 5 subjects in initial group of 12 at Dose Level 0 experience DLT and [Table 10](#) indicates escalation (E) from Dose Level -1 back to Dose Level 0.

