8.3 Hypotheses/Estimation

No formal hypotheses are to be tested in this trial; objectives of the trial are stated in Section 3.

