8.8 Sample Size and Power Calculation

In the Dose Evaluation phase, a minimum of 12 subjects will be evaluated at Dose Level 0.

A potential maximum of 41 subjects may be evaluated across dose levels for DLTs as described in Section 5.2.1.3.4. Twelve subjects evaluated at Dose Level 0 is not entirely based on statistical grounds but would allow for at least 3 evaluated per disease (rrCLL, rrMM, and rrDLBCL) with an overall statistical assessment of the DLT rate as described in [Table 12](#).

In Signal Detection phase, the proposed sample size is 30 subjects for the primary analysis population (ASaT) for each cohort (CLL, MM, DLBCL), 90 in all. With 30 subjects in each cohort, the maximum half-width of the two-sided 95% exact confidence interval for ORR within each cohort is 19%. [Table 20](#) describes examples of 95% confidence intervals per cohort across a possible range of ORRs.

Table 20 Precision (95% Confidence Intervals) for Range of Observed ORR (33% - 83%)

Number of responses/Number of treated subjects (ORR)	95% 2-sided Confidence Interval ^a
10/30 (33%)	(17, 53)
15/30 (50%)	(31, 69)
20/30 (67%)	(47, 83)
25/30 (83%)	(65, 94)

^a exact (Clopper-Pearson) confidence limit for the binomial proportion.
Abbreviation: ORR = objective response rate.

Thus, the minimum and maximum overall sample size for this trial is 102 and 131 subjects, respectively, 12 to 41 subjects from Dose Evaluation plus 90 from Signal Detection. Assuming a 5% non-evaluable rate (ie, not evaluable for DLT in Dose Evaluation or not treated in Signal Detection), a maximum of 138 subjects would be enrolled in this trial.

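### Table 12's one-sided p-values are shifted by one count: each row holds the values for one more DLT than its label states

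*Combined protocol and SAP*

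**What the plan says.** Section 5.2.1.3.4 opens Signal Detection if 4 or fewer of the 12 subjects at Dose Level 0 have a DLT. It then presents Table 12, titled "Probability of Observing the Number (%) of Subjects with DLT". The rows are labelled by observed number, 2 (16.7%) to 6 (50.0%). The columns are assumed true rates θ0 of 0.20 to 0.40, and the column heading marks the entries as p-values. The text tells the reader how to take the entries: "which can be interpreted as the one-sided p-values for testing the null hypothesis that the true DLT rate is less than" (the clause ends with the symbol θ0). The footnote adds: "The probabilities (p-values) for the monitoring of the first 12 subjects were calculated from Binomial distribution".

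The same section limits the weight of the table: "These criteria are considered non-binding guidelines; recommendations would not be based solely on statistical grounds". Section 8.3 states: "No formal hypotheses are to be tested in this trial". Section 8.6.5 refers the reader to Section 8.8 for the statistical details of dose evaluation. Section 8.8 explains the choice of 12 subjects partly as allowing at least 3 per disease "with an overall statistical assessment of the DLT rate as described in" Table 12.

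**The concern.** The stated null is that the true DLT rate lies below θ0, so many DLTs count against it. The one-sided p-value for k observed DLTs is therefore the upper tail including the observed count, P(X ≥ k), evaluated at θ0. The printed entries leave the observed count out.

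DLT is the primary endpoint in the Section 8.1 summary, and Table 12 is what Section 8.8 offers as the statistical assessment of the DLT rate in the first cohort. Anyone who looks up the observed count will read the p-value for a more extreme result than the one seen, and a study report citing the table would repeat the error. What is at stake is that stated assessment, not the dose decision rule.

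**Working it through.** **Inputs.** All come from Section 5.2.1.3.4: n = 12; exact binomial distribution; k = 2 to 6; θ0 = 0.20, 0.25, 0.30, 0.35, 0.40; one-sided, with the null that the rate is below θ0.

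**Step 1: find the formula behind the printed table.** Each candidate was computed for all 25 cells and compared to three decimals.

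| Quantity | Cells matching |
|---|---|
| P(X > k) | 25 of 25 |
| P(X ≥ k), the p-value as described | 0 of 25 |
| P(X = k), the literal reading of the title | 0 of 25 |
| P(X ≤ k) | 0 of 25 |
| P(X < k) | 0 of 25 |
| Mid-p | 0 of 25 |

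Using P(X ≥ k) with n = 11 or n = 13 does not give the table either. The row percentages (2/12 = 16.7% to 6/12 = 50.0%) agree with their counts, so the labels were not displaced when the PDF was read.

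**Step 2: one cell in full.** Take k = 5, θ0 = 0.20.
- P(X = 5) = C(12,5) × 0.2⁵ × 0.8⁷ = 792 × 0.00032 × 0.2097 = 0.0532
- P(X > 5) = 0.0194, which is the printed 0.019
- P(X ≥ 5) = 0.0532 + 0.0194 = 0.0726, the one-sided p-value

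At θ0 = 0.30, the target rate used for Table 13: P(X = 5) = 0.1585 and P(X > 5) = 0.1178 (printed 0.118), so P(X ≥ 5) = 0.2763.

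**Step 3: the row for 5 of 12.** Ratios use unrounded values.

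| θ0 | Printed | P(X ≥ 5) | Ratio |
|---|---|---|---|
| 0.20 | 0.019 | 0.073 | 3.7 |
| 0.25 | 0.054 | 0.158 | 2.9 |
| 0.30 | 0.118 | 0.276 | 2.3 |
| 0.35 | 0.213 | 0.417 | 2.0 |
| 0.40 | 0.335 | 0.562 | 1.7 |

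In the row for 6 DLTs at θ0 = 0.20 the table prints 0.004, where the p-value is 0.019 (0.0194 / 0.0039, about 5-fold).

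**Step 4: the full table of P(X ≥ k).**

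| k | 0.20 | 0.25 | 0.30 | 0.35 | 0.40 |
|---|---|---|---|---|---|
| 2 | 0.725 | 0.842 | 0.915 | 0.958 | 0.980 |
| 3 | 0.442 | 0.609 | 0.747 | 0.849 | 0.917 |
| 4 | 0.205 | 0.351 | 0.507 | 0.653 | 0.775 |
| 5 | 0.073 | 0.158 | 0.276 | 0.417 | 0.562 |
| 6 | 0.019 | 0.054 | 0.118 | 0.213 | 0.335 |

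Rows 3 to 6 are the rows now printed for 2 to 5. The row now printed for 6 belongs to 7 DLTs.

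**Illustration.** The exact one-sided 95% lower bound is 18.1% for 5/12 and 24.5% for 6/12. So 5/12 does not exclude a 20% rate at the 5% level, whereas a p-value of 0.019 would imply that it does. This inverts the same binomial test, so it restates the discrepancy and is not separate evidence. The 5% level is an illustrative choice; the protocol sets no cut-off.

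**The case against.** The strongest reply is that nothing depends on the table. The rule (4 or fewer, 5 or more) is written as counts, Table 13 has its own parameters, the criteria are non-binding, and no p-value threshold exists. Section 8.1 plans only descriptive statistics for the DLT rate, and Section 8.3 rules out formal testing. Section 8.8 mentions Table 12 while explaining a sample size that it says is not wholly statistical. All of this stands, and it limits the consequence.

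The numbers are also correct under another description. Read as the probability of more than k DLTs, the row for 4 is exactly the chance of reaching the 5-or-more trigger, a useful operating characteristic. But the protocol nowhere gives that description. The observed-number heading and the p-value sentence both contradict it.

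Two further points are fair. The error makes a given count look more toxic than the data support, so it cannot make an unsafe dose look safe. And the first cohort at Dose Level 0 needs at least 3 subjects each with rrCLL and rrMM, both now closed to enrollment. The practical effect is therefore mainly on how the result is read and reported. These points bear on how serious the error is, not on whether the table is right.

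**Conclusion.** The concern holds. Every entry in Table 12 is P(X > k), while the row labels and the text present it as the one-sided p-value for k observed DLTs, so each row holds the values for k + 1. At 5 of 12 the printed values are too small by a factor of 1.7 to 3.7, and by 2.3 at the 30% target rate. The conclusion rests only on the protocol's own n = 12, its binomial model, and the usual definition of a one-sided p-value as including the observed result. The effect is confined to the stated statistical assessment of the DLT rate. The decision counts, Table 13, the sample size and the planned analyses are unchanged. It should be fixed, because the protocol points to these figures and they do not mean what it says they mean.

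**What to change.** Choose one:

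- **(a) Correct the cells.** Replace them with P(X ≥ k) as tabulated above, and retitle the table as the probability of observing k or more DLTs. The row for 2 DLTs needs new values (0.725, 0.842, 0.915, 0.958, 0.980). Every other row takes the values now printed one row higher.
- **(b) Correct the labels.** Keep the cells, label the rows and title as more than k DLTs, and delete the p-value sentence and the p-value wording in the column heading and footnote. This also fits Section 8.3, and I would prefer it for that reason.

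Under either option it would help, though it is not essential, to state that the values now in the row for 4 are the probabilities of reaching the 5-or-more trigger: 7.3%, 15.8%, 27.6%, 41.7% and 56.2% at true rates of 20%, 25%, 30%, 35% and 40%.

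The cost is a table or label correction. It needs no extra subjects and changes no decision count, Table 13 entry or planned analysis.

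### An E at Level -1 re-opens Level 0 with no upper limit on its DLT count, so a Level 0 that Table 13 codes DU (7 or more DLTs in 12) is re-entered as written

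*Combined protocol and SAP*

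**What the plan says.** All of this is in Section 5.2.1.3.4.

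- **Leaving Level 0.** Five or more DLTs at Level 0 send dosing to Level -1. Higher counts have no separate branch.
- **Returning to Level 0.** An E at Level -1 "would trigger an increase to Level 0 and would resume at the number of subjects where it previously left off"; if Level 0 stopped at 12, it goes on with subjects 13 to 17.
- **Table 13 footnote a.** "subjects 13-17 are only used to evaluate Dose Level 0 if ≥ 5 subjects in initial group of 12" have a DLT and the guidance shows an E from Level -1. These are the only conditions.
- **Exposure on return.** "a maximum of 5 additional subjects will be evaluated at Dose Level 0, up to 17 subjects in all".
- **Meaning of DU.** The key reads "DU = Current dose level is unacceptably toxic". No sentence attaches an action to it.
- **Returning to Level -1.** After an E at Level -2, "enrollment and evaluation will continue at Level -1 from where it previously left off".
- **Who decides.** "All decisions regarding dose levels for subject enrollment and dosing will be made by the Sponsor". A sentence introducing Table 12 also calls the criteria there non-binding.

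**The concern.** Table 13 has one code for a level to step down from (D) and another for a level that is too toxic (DU). The return rule treats them alike. A Level 0 left at 9/12 is re-opened by the same E as one left at 5/12.

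The E can be thin evidence. Table 13 gives E for 0 DLTs in the first 3 subjects at Level -1. At a true Level -1 rate of 30% that has probability 0.7³ = 0.343. Levels 0 and -1 also share both Cycle 1 doses (Table 11) and differ only from Cycle 2 Day 1, so three clean subjects at Level -1 say little against 7 or more DLTs in 12 at Level 0.

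What is at stake is subject safety: up to 5 further subjects dosed at a level that the plan's own guidance calls too toxic, or 1 if the guidance is read after each subject. DLT is the primary endpoint in Section 8.1, but it is summarised descriptively and no hypothesis is tested (Section 8.3), so no inference depends on this rule.

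**Working it through.** **1. Is 7/12 really DU?** The Table 13 inputs are "Target DLT rate = 30%; a=.05, b=.05, k1=1.25; k2=0.5; pow=1". The posterior for the DLT rate after x DLTs in n is Beta(0.05 + x, 0.05 + n - x). The DU cut-off is not stated; I assume P(rate > 0.30) > 0.95. With the interval rule this reproduces 135 of 137 legible cells. The two misses, 3/12 and 6/13, play no part here.

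| Count | P(rate > 0.30) | Table 13 code |
|---|---|---|
| 5/12 | 0.792 | S |
| 6/12 | 0.923 | D |
| 7/12 | 0.979 | DU |
| 7/13 | 0.962 | DU |
| 8/13 | 0.991 | DU |

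In the available text the table rows hold 16 entries over 15 numbered columns, with an unlabelled column after 12. I read columns 13-17 both ways. Column 12 is unaffected, and 7/13 and 8/13 are DU either way.

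**2. What can subjects 13-17 show?**
- From 7/12, S needs no DLT in the next 4 subjects (7/16) or the next 5 (7/17), depending on the column reading.
- From 8/12, the best result is 8/17, coded D at best.
- From 9/12 or more, every attainable count is DU.

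**3. How often does Level 0 end at DU?** X ~ Binomial(12, p). The documents give no expected DLT rate, so p is assumed.

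| p | P(X = 7) | P(X ≥ 7) | P(X ≥ 8) |
|---|---|---|---|
| 0.30 | 0.0291 | 0.0386 | 0.0095 |
| 0.40 | 0.1009 | 0.1582 | 0.0573 |
| 0.50 | 0.1934 | 0.3872 | 0.1938 |

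Table 12 confirms the first two tails: its row for 6 DLTs prints 0.039 and 0.158 at 0.30 and 0.40, which are the probabilities of more than 6.

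**4. How often does Level -1 give E?** I walked the Table 13 codes exactly from n = 3 to 12, stopping at the first E, D or DU and otherwise adding 3 subjects or 1 (the step is not stated; the two choices give the ends of each range). P(E) = 0.784-0.851, 0.561-0.683, 0.350-0.498 and 0.190-0.324 at rates 0.2, 0.3, 0.4 and 0.5.

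**5. Joint chance** = P(X ≥ 7) × P(E).

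| Level 0 rate | Level -1 at the same rate | Level -1 10 points lower |
|---|---|---|
| 0.30 | 0.0386 × 0.561 to 0.683 = 2.2-2.6% | 3.0-3.3% |
| 0.40 | 0.1582 × 0.350 to 0.498 = 5.5-7.9% | 8.9-10.8% |
| 0.50 | 0.3872 × 0.190 to 0.324 = 7.3-12.6% | 13.5-19.3% |

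Returns that pass through Level -2 are not counted.

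**6. What would a bar forgo at a true 30% rate?**
- *Twelve subjects always enrolled.* The bar applies in 3.9% of trials. Recovery to S has probability 0.0291 × 0.7⁵ to 0.0291 × 0.7⁴ = 0.0291 × 0.168 to 0.240 = 0.5-0.7%.
- *Level 0 stops at its fifth DLT.* Counts 5/5, 5/6, 5/7 and 5/8 are DU, with total probability P(5 or more of 8) = 5.8%. Walking Table 13 one subject at a time, Level 0 reaches S in 51-58% of these with a cap of 17 subjects, or 27-38% with 5 additional subjects. Forgone recovery is 0.058 × 0.27 to 0.58 = 1.6-3.4%.

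Both are before P(E) of 0.56-0.68. After it they become 0.3-0.5% (0.0049 × 0.561 to 0.0070 × 0.683) and 0.9-2.3% (0.0157 × 0.561 to 0.0335 × 0.683).

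**The case against.** **Discretion.** Table 13 is headed as guidance, additional subjects may (not must) be enrolled, the trial team reviews safety data (Section 2.1), the Sponsor decides on every dose level, and Section 5.11 allows termination for unacceptable risk. This stands as far as it goes: a reader might infer that dosing at a DU level is automatic, and the documents do not support that. But discretion only permits a departure. The non-binding sentence is attached to the Level 0 go rule and Table 12, and the return rule itself carries no exception.

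**DU must mean more than D.** A separate code suggests a stronger meaning, and the design is based on a cited method that may exclude such doses. That method cannot be checked here. The protocol writes out its own return rules without the exclusion.

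**The bar costs more if Level 0 can stop early.** This stands. The phrase about resuming where Level 0 left off contemplates a stop before 12, while footnote a and the references to an initial 12 point the other way. On the early-stop reading, returning subjects can have real decision value: 5/8 becomes 5/11, coded S, after three subjects without a DLT. Both costs are therefore given.

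**Level -1.** A reader might infer the same defect for the return from Level -2 to Level -1, for instance after 3/3. The text does not support it. Only a D sends Level -1 to Level -2, so no stated route leaves Level -1 at DU. That exit is undefined, which calls for a clarification and has no probability to attach.

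**Timing.** rrMM closed in August 2017 for lack of efficacy with no safety concerns, rrCLL closed in April 2019 for lack of accrual, and the current amendment serves to end the study. Dose Evaluation is probably over, though the documents do not say so.

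**Conclusion.** The point holds for Level 0. Read literally, Section 5.2.1.3.4 and footnote a send new subjects back to a Level 0 coded DU. It does not follow that any return after 5 or more DLTs is wrong: 5/12 and 6/12 are coded S and D, and return from them is consistent with the table.

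With 12 subjects at Level 0, the route occurs in 2.2-2.6% of trials when both levels have a true 30% DLT rate, and in 7.3-12.6% when both have 50%. It is more frequent if Level -1 is less toxic. In 25%, 36% and 50% of the DU cases at 30%, 40% and 50% (0.0095/0.0386, 0.0573/0.1582, 0.1938/0.3872), S is already out of reach. Over all DU re-entries, the chance that Level 0 reaches S is 13-18%, 5-8% and 1.6-3.1%.

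These figures rest on assumed DLT rates, independent subjects, and an assumed step size at Level -1. The statement that re-entry seldom informs the decision is limited to the 12-subject reading. This is a cheap improvement to a subject-safety rule. If Dose Evaluation has ended, it corrects standing text only.

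**What to change.** Add to Section 5.2.1.3.4, and as a condition in Table 13 footnote a:

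> Dose Level 0 is not re-entered if its current count is coded DU in Table 13; an E at Level -1 then means stay at Level -1. After 12 subjects at Level 0, return is allowed only with 5 or 6 DLTs.

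As a clarification only, state what DU requires at Level -1 and at Level -2, and whether Level 0 always enrols 12 or stops at the fifth DLT.

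**Cost.** Two or three sentences. The 41-subject maximum (17 + 12 + 12) is unchanged, because 5/12 and 6/12 can still return. At a true 30% rate the bar would apply in 3.9% of trials with 12 always enrolled, or 5.8% with stopping at the fifth DLT; working step 6 gives the forgone recoveries. Later cells that would allow a Level 0 with 7 DLTs to continue, such as 7/16 as printed, are given up when the count at 12 was already 7.

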5.2.1.4 Definition of Dose-Limiting Toxicity

DLTs will be defined from toxicities observed during Cycles 1 and 2. The occurrence of any of the following toxicities during these periods, if assessed by the investigator to be possibly, probably, or definitely related to pembrolizumab or dinaciclib will be considered a DLT:

1. Grade 4 nonhematologic toxicity (not laboratory)
2. Grade 4 hematologic toxicity lasting > 7 days, except thrombocytopenia
 - a. Grade 4 thrombocytopenia of any duration
 - b. Grade 3 thrombocytopenia is a DLT if associated with bleeding;
3. Any Grade 3 nonhematologic toxicity (not laboratory), with the exception of Grade 3 nausea, vomiting, or diarrhea, which will not be considered a DLT unless lasting more than 3 days despite optimal supportive care.
4. Any Grade 3 or Grade 4 nonhematologic laboratory abnormality, if:
 - medical intervention is required, or
 - the abnormality leads to hospitalization, or
 - the abnormality persists for > 1 week
5. Febrile neutropenia Grade 3 or Grade 4
6. Any drug-related AE which caused subject to discontinue treatment during Cycles 1 or 2
7. Grade 5 toxicity
8. Any treatment-related toxicity which causes a > 2-week delay in initiation of Cycle 2 or Cycle 3

